HI4T trial

Prospective, parallel-group, open-label randomized
controlled trial of four treatment regimens for trichuriasis
in pediatric patients

NCT04041453

Protocol version 1.0

29NOV2018

HI4T Trial - PROTOCOL SYNOPSIS

STUDY IDENTIFICATION	Prospective, parallel-group, open-label randomized controlled trial of four treatment regimens for trichuriasis in pediatric patients. HI4T trial.
TYPE AND DEVELOPMENT CLINICAL PHASE	Phase II non-inferiority randomized clinical trial
SPONSOR	Fundacion Mundo Sano, Spain
INVESTIGATOR	[name], Principal Investigator [name], PhD. General Coordination
STUDY CENTERS	
 • Universidad Autonoma de Honduras Laboratory centers: 
 • Genetics Research Center. UNAH, Tegucigalpa, Honduras • [name] lab. CIVETAN, UNCPBA - Tandil, Argentina (pk). • [name] lab, IIET, UNSa – Orán, Argentina (resistance)
ETHICAL COMMITTEE APPROVAL	CEI-MEIZ, UNAH, HON & Brock University, Canada.
OBJECTIVES	
Primary endpoints Cure rate (CR) (conversion from being egg positive pre-treatment to egg negative post-treatment) for Trichuris infection will be assessed using the quadruple Kato-Katz method at 14 to 21 days post-treatment.
 
Secondary endpoints
 
 • To evaluate the safety and tolerability of the interventions. • To measure the egg reduction rate of the different treatment arms against T. trichiura. • To validate the multi-parallel qPCR for the determination of efficacy outcomes. • To determine the presence of isolates with resistance to the study drugs in the pre and post treatment isolates. • To determine population pk parameters of IVM through a population pk approach.
DESIGN AND METHODOLOGY	Phase II, open label randomized, controlled, parallel groups clinical trial in patients infected with T. trichiura .

TREATMENT ARMS	
 • Group 1: single dose of ALB 400 mg. (active control arm). N:39 • Group 2: single dose ALB 400mg + IVM 600µg/Kg. N: 57 • Group 3: daily dose ALB 400mg for 3 consecutive days. N:24 • Group 4: daily dose ALB 400mg + IVM 600µg for 3 consecutive days. N:57 
Total Study Population: 177

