Alanine transaminase (ALT) and aspartate transaminase (AST) levels will be determined by a private clinical laboratory, which will receive the anonymized samples (bearing only the participant identification code). The reference values will be determined by the laboratory but the most common ones are of the following ranges:

ALT = 0 – 40 U/L

AST = 0 – 40 U/L

Should there be any participant with altered hepatic enzymes, they will be examined clinically and undergo another test at the end of the study.

Establishing Parasitic Infection

Stool samples from study participants will be collected and kept refrigerated in coolers. Same day analysis will be done via the Kato-Katz method, following WHO recommendations. A total egg count for each helminthic species will be done and expressed as the number of eggs per gram (EPG) of stool. Based on the EPG, an intensity of infection will be determined, including the categories light, moderate or heavy. Aliquots of each sample using each 95% ethanol and 10% formalin will be preserved for molecular analysis and diagnosis of protozoan infection, respectively.

Treatment Efficacy

To determine treatment efficacy, a method determining “cure rate” (CR) will be used. Cure rate is defined the percentage of subjects who no longer pass eggs after treatment (with a 0-egg count per gram of stool at the end of the treatment period). The formula is as follows:

$$CR = 100\% \times \left(1 - \frac{\text{number of subjects excreting eggs at follow-up}}{\text{number of subjects excreting eggs at baseline}} \right)$$

Comparison of Kato Katz vs multi-panel qPCR for evaluating treatment efficacy

A quantitative qPCR analysis will be done for the determination of intensity of infection in the stool samples provided by the participants, with the purpose being to compare these results with those of the Kato Katz technique. The agreement between both methods will be estimated using the Kappa statistic, which sets out to measure level of agreement between techniques. Values of $\kappa = 0, 0.01-0.20, 0.21-0.4, 0.41-0.60, 0.61-0.80, 0.81-1$ are interpreted as poor agreement, light agreement, moderate agreement, considerable agreement and excellent agreement, respectively.

Identification of genetic mutations associated with BZ resistances before and after treatment

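### The kappa scale for validating qPCR has six ranges but only five labels, and the plan does not say which samples or coding kappa uses

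*Combined protocol and SAP*

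**What the plan says.** The synopsis lists as a secondary endpoint "To validate the multi-parallel qPCR for the determination of efficacy outcomes". The method is in the protocol section on comparing Kato-Katz with qPCR for evaluating treatment efficacy:

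- On the measurement: "A quantitative qPCR analysis will be done for the determination of intensity of infection in the stool samples provided by the participants".
- On the statistic: "The agreement between both methods will be estimated using the Kappa statistic".
- On its reading: six kappa entries (0; 0.01-0.20; 0.21-0.4; 0.41-0.60; 0.61-0.80; 0.81-1), which "are interpreted as poor agreement, light agreement, moderate agreement, considerable agreement and excellent agreement, respectively".

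The section names no visit, sample set, coding (positive/negative or intensity class) or weighting. The list of participant procedures has stool collected before treatment and again 14-21 days after it. In the section on establishing infection, Kato-Katz gives an egg count, from which "an intensity of infection will be determined, including the categories light, moderate or heavy". The primary endpoint in the synopsis is "conversion from being egg positive pre-treatment to egg negative post-treatment", so it takes every randomised child as egg positive at the start.

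**The concern.** There are two separate defects.

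First, the word *respectively* requires one label per entry, and there is one label too few. The same kappa can therefore be given different words depending on where the reader puts the gap, and that choice could be made after the data are seen. The endpoint claims validation, and these words are the only guide to what the kappa value means.

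Second, kappa needs variation on both tests. Randomised children are selected for *T. trichiura* infection, so a positive/negative table of their baseline samples has an empty Kato-Katz-negative row. If that table is analysed, or pooled with follow-up, the result is uninformative about agreement on cure, or mixes that agreement with qPCR sensitivity in children already known to be positive.

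**Working it through.** **1. The scale.** Pairing entries and labels in printed order:

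| Kappa | Label as printed |
|---|---|
| 0 | poor |
| 0.01-0.20 | light |
| 0.21-0.4 | moderate |
| 0.41-0.60 | considerable |
| 0.61-0.80 | excellent |
| 0.81-1 | none |

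Values below 0 have no label either. Both lists stand complete in one sentence, and no other section repairs the mapping.

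**2. The plan's own numbers.** The sample-size table gives 35 + 51 + 51 + 21 = 158 children before inflation. Dividing each by 0.9 and rounding up gives 39 + 57 + 57 + 24 = 177, as stated. So take 177 baseline samples and about 158 at follow-up.

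**3. Baseline, positive/negative coding, randomised children.** Let *n* = 177, all Kato-Katz positive, with *a* of them qPCR-positive.

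- Observed agreement: po = a/n.
- Chance agreement: pe = (n/n)(a/n) + (0/n)((n − a)/n) = a/n.
- Kappa = (po − pe)/(1 − pe) = 0 whenever a < n, and 0/0 (undefined) when a = n.

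With a = 170, po = pe = 170/177 = 0.960 and kappa = 0, despite 96% raw agreement.

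**4. Follow-up at the planned cure rates.** Expected Kato-Katz negatives: 0.17×35 + 0.55×51 + 0.60×21 + 0.85×51 = 5.95 + 28.05 + 12.60 + 43.35 = 89.95. Expected positives: 158 − 89.95 = 68.05.

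**5. Pooling.** The documents give no qPCR rates, so these are assumptions. Cells are in the order both positive / Kato-Katz positive only / qPCR positive only / both negative. Pooling adds all 177 baseline samples to the first two cells.

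*Scenario A:* qPCR positive in 100% of follow-up and 98% of baseline Kato-Katz positives, and in 30% of follow-up Kato-Katz negatives.

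- Follow-up: 68.05 / 0 / 26.99 / 62.97. po = 0.829, pe = 0.486, kappa = 0.343/0.514 = 0.67.
- Pooled (n = 335): 241.51 / 3.54 / 26.99 / 62.97. po = 0.909, pe = 0.640, kappa = 0.269/0.360 = 0.75.

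*Scenario B:* qPCR positive in 90% of Kato-Katz positives at both visits, and in 5% of follow-up Kato-Katz negatives.

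- Follow-up: 61.25 / 6.81 / 4.50 / 85.45. po = 0.929, pe = 0.512, kappa = 0.417/0.488 = 0.85.
- Pooled: 220.55 / 24.51 / 4.50 / 85.45. po = 0.913, pe = 0.579, kappa = 0.334/0.421 = 0.79.

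Pooling raises kappa in A and lowers it in B. In B it also crosses from the top range into the one below. With 90% at both visits and 20% among negatives, it barely moves (0.69 to 0.68).

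**6. Other readings that the text allows.** Kappa is not degenerate under these:

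- Three intensity classes in 177 Kato-Katz positives: an invented table with po = 0.746 and pe = 0.482 gives 0.264/0.518 = 0.51.
- All pre-treatment survey samples: at least 295 children at 60% prevalence is 177 positive and 118 negative. With qPCR positive in 95% and 5% respectively, po = 0.950, pe = 0.518 and kappa = 0.90. With 90% and 30%, po = 0.820, pe = 0.532 and kappa = 0.62.

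**The case against.** The strongest reply is that the plan never commits to a positive/negative kappa at baseline. It describes qPCR as a measure of intensity and has intensity classes for Kato-Katz. Its pre-treatment survey includes uninfected children, and the section heading and the endpoint both refer to efficacy, which points to follow-up. This stands: the zero-or-undefined result is conditional. It does not remove the gap, because the plan does not choose among these readings, and they give anything from 0 to about 0.90 under the assumptions above.

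A reader might also infer that the printed scale inflates every result by one grade. The documents do not support that. They do not show which label is missing. If the authors meant the last label for 0.81-1, high values are not over-graded; and as printed, a value in 0.81-1 gets no grade at all. Nor is pooling shown to favour qPCR, since its direction depends on the assumed sensitivity.

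Finally, the words are descriptive. The plan sets no kappa threshold for success, and the numerical kappa can be read without them. That stands too, and it limits the importance of the point.

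**Conclusion.** The scale is wrong as written: six entries, five labels, and no label for the highest agreement. This follows from the text alone and needs no assumption.

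The sample set and coding for kappa are unspecified. The consequence at baseline (0, or undefined at 177 of 177) is exact, but only for positive/negative coding in randomised, Kato-Katz-positive children. The pooling examples (0.67 to 0.75; 0.85 to 0.79) rest on assumed qPCR rates and the planned cure rates. They show that pooled kappa depends on more than agreement about cure, not that it is biased in one direction.

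This is a minor issue on a secondary endpoint. It does not touch the primary endpoint, the sample size or safety.

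**What to change.** 1. Give six labels for the six ranges. For example, add one (such as fair) for 0.21-0.40, so that 0.41-0.60 is moderate, 0.61-0.80 considerable and 0.81-1 excellent. Treat values below 0 as poor. Where the new label goes is the authors' choice, but it should be fixed before the data are seen.
2. For the efficacy validation, compute unweighted kappa on egg-positive/egg-negative status by each method, using the day 14-21 samples only. Report baseline as the percentage of Kato-Katz positives that are qPCR-positive, with a confidence interval. If agreement on intensity class is also wanted, name it as a separate analysis with its categories and weighting.

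Cost: about two sentences of wording, and a smaller sample set for kappa (about 158 expected completers, against 335 samples if both visits were pooled). No new samples or assays are needed.
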